Since ferumoxytol is a “blood pool agent” (i.e. providing long lasting vascular enhancement), it is not crucial for the quality of the imaging scan to administer the contrast agent while the patient is in the scanner or to start a post-contrast scan immediately after contrast media administration. Thus, we will hand-inject ferumoxytol slowly into a peripheral vein while the patient is outside of the MR scanner and under direct supervision. We will observe the patient for a few minutes, acquire vital signs and ask him/her for any subjective adverse effects before we continue the imaging scan. We will continue to observe the patient closely and record heart rate and respiratory rate continuously during the MR scan. Blood pressure and temperature will be monitored before, directly after contrast media injection as well as at the end of the MR scan. The patient will be monitored up to 90 minutes after the contrast media administration. These data will be recorded according to the following table, which is part of the case report form:

Patient Name:	Patient weight:						
Birth Date:	Ferumoxytol dose (5 mg/kg):						
Medical Record #:	Ferumoxytol volume: = weight (kg) x dose (5 mg Fe/kg) / 30 mg Fe/ml						
Ferumoxytol injection, date (dd/mm/yyyy) and start time (hh/min):							
Ferumoxytol injection end time (hh/min):							
Planned injection rate: 10 ml / min	Actual injection rate:						
Contrast agent completely injected: yes / no	Actual injection volume:						
Evidence of paravasal injection: yes / no	Local Reaction at injection site: yes / no						
Vital signs:	pre	0 min	15 min	30 min	45 min	60 min	90 min
Heart Rate							
Respiratory rate							
Blood pressure							
Temperature							
Any objective or subjective adverse reaction (time):							
Any objective or subjective adverse reaction (describe):							

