6. DOSE MODIFICATIONS

Dose modification scheme:

- (A) Serious anaphylactoid reactions are not dose dependent. Thus, in case we should observe an increased incidence of severe anaphylactoid reactions, i.e. more than one patient in our limited study population of 20 patients, or if any of our patients encounters a permanent impairment due to the ferumoxytol administration, the study will be terminated.
- (B) In case we should observe an unexpected decrease in blood pressure of more than 10% in more than one patient via blood pressure measurements or in case we observe severe nausea in more than one patient, we will successively decrease the administered dose by 1 mg/kg until event-free tolerance is achieved. Of note, our colleagues from Oregon Health & Science University (see below) reported no such side effects of ferumoxytol in their population of children with brain tumors.
- (C) Precontrast MR scans will serve as an internal standard. We will measure the signal intensity of sarcomas and osteomyelitis and divide this signal by the signal of normal muscle to normalize for potential MR spectrometer variations over time. We expect at least 20% tumor/muscle enhancement on post-contrast T2-weighted MR scans compared to precontrast scans. If this enhancement will not be achieved, but ferumoxytol is well tolerated, we will increase the administered dose to 6 mg Fe/kg with a maximum total amount of 510 mg Fe (FDA-approved dose for single injection).

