- (D) In the unlikely event, that the T1- and T2-enhancement of both pathologies exceeds 500%, we have reached a plateau of contrast agent accumulation for both pathologies rather than depicting an expected relative limited accumulation of ferumoxytol in sarcomas compared to osteomyelitis. Based on our experience with pre-clinical and clinical iron oxide applications, we expect that maximal difference between sarcomas and osteomyelitis occur with the highest dose. This is the reason why we limit our study population to this dose for this initial pilot study. In the unlikely event that contrast agent accumulation reaches a plateau in both of these pathologies or no enhancement is noted on MR scans, we will terminate the study after evaluation of n=6 patients (MR data from n=6 patients should allow evaluation of significant differences between quantitative pre- and post-contrast signal intensities via a t-test). We have submitted an R21 NIH grant proposal which would allow more extensive evaluation of patient subgroups (n=5), examined with decreasing ferumoxytol doses.

Stopping rules for an individual test:

- (A) To avoid paravasal injections, the peripheral venous access will be checked with a saline flush prior to contrast media injection. In case of any swelling or discoloration at the ferumoxytol injection site (in the extremely rare event of a paravasal injection despite prior uncomplicated saline injection), the ferumoxytol injection will be stopped immediately, a new peripheral venous access will be placed at the contralateral extremity and the remaining ferumoxytol will be slowly administered. In case a local reaction is observed again, the ferumoxytol injection will be discontinued completely.

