- (B) If we observe a decline in blood pressure during the contrast media injection, we will discontinue the ferumoxytol injection immediately (in the experience of the PI, a transient hypotension represents a possible AE). In case we observe any signs of a potential anaphylactoid reaction (e.g. significant hypotension > 10% with associated tachycardia or bradycardia) during the contrast media injection, the injection will be discontinued immediately. Patients with mild symptoms such as urticaria, pruritus, rhinorrhea, nausea, diaphoresis and/or coughing will be observed for resolution of symptoms or progression. Patients, who show severe and/or progressive symptoms, such as arrhythmias, severe hypotension, breathing difficulties, dizziness or vomiting will be treated immediately by the M.D. on site and the Pediatric Emergency Care team will be

notified for immediate assistance.

Stopping rules for the study:

- (A) In case of any serious AE, that leads to persistent impairment of a study patient, the study will be terminated.
- (B) Anaphylactoid reactions are a possible, but rare side effect of any contrast agent, reported in 1% of patients receiving Gd-based contrast agents and 1% of patients receiving ferumoxytol. In case we observe an increased incidence of severe anaphylactoid reactions, i.e. more than one patient in our limited study population of 20 patients, the study will be terminated.
- (C) According to our statistician, the study population of n=10 patients with sarcomas and n=10 patients with osteomyelitis is already very limited and considered a pilot population to demonstrate major differences in ferumoxytol enhancement of these two pathologies. In the unlikely event, that contrast enhancement reaches a plateau in both pathologies or no enhancement at all is noted in these pathologies on MR scans, neither on T2-weighted MR scans nor on T1-weighted MR scans, the study will be terminated after evaluation of n=6 patients (MR data from n=6 patients should allow evaluation of significant differences between quantitative pre- and post-contrast signal intensities via a t-test).

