APPENDIX B: Case Report Forms**I. Patient History**

Patient Name:	Medical Record #:	
Birth Date:	Patient body weight:	
Gender:	Patient height:	
Medications:	Allergies:	
Inclusion Criteria:		
Age: 10-21 years	yes	no
suspected or confirmed diagnosis of a bone sarcoma or osteomyelitis	yes	no
Exclusion Criteria:	yes	no
Hemosiderosis/Hemochromatosis	yes	no
History of any allergies to contrast agents or any severe allergies to other substances	yes	no
Claustrophobia	yes	no
MR-incompatible metal implants	yes	no
Any significant previous illnesses or injuries: (date / completed or ongoing)	Any previous surgeries: (date / completed or ongoing)	
CNS:	CNS:	
Head/Neck:	Neck:	
Chest:	Chest:	
Abdomen/Pelvis:	Abdomen/Pelvis:	
MSK:	MSK:	
Psychological / Emotional:	Psychological / Emotional:	
Other:	Other:	
Details:		

II. Physical Examination

Patient Name:	Medical Record #:		
Patient body weight:	Patient height:		
Blood Pressure:	Pulse rate:		
ECG date (within 30 d prior to Ferumoxytol MR):			
ECG report (summary):			
Clinical Evaluation:	normal	abnormal	Describe abnormal findings
CNS			
Head/Nose/Mouth			
Ears			
Eyes			
Neck			
Lungs / Auscultation			
Heart / Auscultation			
Abdomen			
Pelvis			
Spine			
Upper Extremities			
Lower Extremities			
Skin			
Pregnancy test (within 24 h prior to contrast media injection):			
Other:			

III. Contrast Media Administration

Patient Name:	Patient weight:						
Birth Date:	Ferumoxytol dose (5 mg/kg):						
Medical Record #:	Ferumoxytol volume: $= \text{weight (kg)} \times \text{dose (5 mg Fe/kg)} / 30 \text{ mg Fe/ml}$						
Ferumoxytol injection, date (dd/mm/yyyy) and start time (hh/min):							
Ferumoxytol injection end time (hh/min):							
Planned injection rate: 10 ml / min	Actual injection rate:						
Contrast agent completely injected: yes / no	Actual injection volume:						
Evidence of paravasal injection: yes / no	Local Reaction at injection site: yes / no						
Vital signs:	pre	0 min	15 min	30 min	45 min	60 min	90 min
Heart Rate							
Respiratory rate							
Blood pressure							
Temperature							
Any objective or subjective adverse reaction (time):							
Any objective or subjective adverse reaction (describe):							

IV. MR Imaging

Acquired pulse sequences			
Date of MR 1 (dd/mm/yyyy):			
Date of MR 2 (dd/mm/yyyy):			
	precontrast	1-60 min p.i.	24 h p.i.
T1-SE			
STIR			
T2-TSE			
T2*-GE			
Other (specify)			
Other (specify)			

(add pulse sequence parameters: TR/TE/alpha/slice thickness/orientation)

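### The 510 mg Fe single-injection maximum is attached only to the 6 mg/kg step, so the planned 5 mg/kg dose has no ceiling, and the administration form is pre-filled for 5 mg/kg only.

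*Combined protocol and SAP*

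**What the plan says.** **Planned dose.** Sections 2.4, 4 (drug administration) and 5.1 set one intravenous injection of 5 mg Fe/kg. None of them gives a maximum amount. Section 4 works the dose through for 50-80 kg at 30 mg Fe/ml and arrives at 250-400 mg Fe, or 8.3-13.3 ml. Section 6(D) explains the choice of a single level: "This is the reason why we limit our study population to this dose for this initial pilot study".

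**Contingent doses.** Section 6(B) responds to blood pressure falls of more than 10%, or severe nausea, in more than one patient: "we will successively decrease the administered dose by 1 mg/kg until event-free tolerance is achieved". Section 6(C) responds to weak enhancement in a well-tolerated setting: "we will increase the administered dose to 6 mg Fe/kg with a maximum total amount of 510 mg Fe (FDA-approved dose for single injection". This is the only place where 510 mg appears.

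**Form.** The administration form is printed in Section 4 and again in Appendix B, part III. Its dose field is labelled "Ferumoxytol dose (5 mg/kg" and its volume field carries the formula "weight (kg) x dose (5 mg Fe/kg) / 30 mg Fe/ml". It also has entries for "Actual injection volume" and "Contrast agent completely injected: yes / no".

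**Eligibility.** Sections 3.1 and 3.2 admit ages 10 to 21 and set no weight limit.

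**The concern.** Section 6(C) describes 510 mg Fe as the approved amount for a single injection. That is a property of the product and has nothing special to do with the 6 mg/kg step. As drafted, though, the limit governs only the step that may never be used, while the dose every patient is due to receive has none. For a heavy enough patient the rules run backwards: the planned dose exceeds the protocol's own named limit, and increasing the dose would reduce the amount given.

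The form adds a secondary problem. It is the worksheet from which the volume is calculated, and it carries the planned level as a fixed value although Section 6 provides for others. If a level changes and the form does not, worksheet and protocol disagree. After a 6(B) reduction the disagreement is towards too much agent, at a time when tolerance is already in question.

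What is at stake is agreement between the dosing instructions and the protocol's own limit. Sample size, endpoints and analysis are not touched.

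**Working it through.** **Inputs.** Dose 5 mg Fe/kg (Sections 2.4, 4, 5.1); concentration 30 mg Fe/ml and anticipated weights 50-80 kg (Section 4); reductions in 1 mg/kg steps, and an increase to 6 mg/kg with a 510 mg maximum (Section 6(B) and (C)).

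**Formulas.** Amount (mg) = weight × dose level. Volume (ml) = amount / 30. Weight at which 510 mg is reached = 510 / dose level.

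**The plan's own figures.** 50 × 5 = 250 mg, and 250 / 30 = 8.3 ml. 80 × 5 = 400 mg, and 400 / 30 = 13.3 ml. Both match Section 4.

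**Where the maximum would bind.** 510 / 30 = 17 ml. At 6 mg/kg it is reached at 510 / 6 = 85 kg; at 5 mg/kg, at 510 / 5 = 102 kg. At 80 kg the planned dose leaves 510 − 400 = 110 mg of room.

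**Amounts under the rules as written** (maximum applied at 6 mg/kg only):

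| Weight | 4 mg/kg | 5 mg/kg (also what the form's formula gives) | 6 mg/kg, capped |
|---|---|---|---|
| 50 kg | 200 mg, 6.7 ml | 250 mg, 8.3 ml | 300 mg, 10.0 ml |
| 80 kg | 320 mg, 10.7 ml | 400 mg, 13.3 ml | 480 mg, 16.0 ml |
| 85 kg | 340 mg, 11.3 ml | 425 mg, 14.2 ml | 510 mg, 17.0 ml |
| 102 kg | 408 mg, 13.6 ml | 510 mg, 17.0 ml | 510 mg, 17.0 ml |
| 110 kg | 440 mg, 14.7 ml | 550 mg, 18.3 ml | 510 mg, 17.0 ml |

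At 110 kg the planned dose is 550 − 510 = 40 mg over, and 40 / 510 = 7.8%. In that row the higher level delivers less than the planned one.

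**Form left unchanged after a Section 6 change.**

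- Reduction to 4 mg/kg: 5 / 4 = 1.25, so the formula gives 25% too much. As the protocol stands this holds at any weight, because no maximum applies at either level. The excess is 250 − 200 = 50 mg at 50 kg and 400 − 320 = 80 mg at 80 kg.
- Increase to 6 mg/kg: 5 / 6 = 0.833, so the formula gives 16.7% too little up to 85 kg. Above 85 kg the correct amount stays at 510 mg, so the shortfall narrows and disappears at 102 kg.

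**The case against.** The best reply on the maximum is that it sits where it could plausibly matter. At 6 mg/kg it binds just above the anticipated range (85 kg against 80 kg); at 5 mg/kg it needs more than 102 kg. A physician who reads in Section 6(C) that 510 mg is the approved single-injection amount would probably treat it as a general ceiling. This bears on likelihood and keeps the point small. It does not supply the missing limit: no section states a maximum at 5 mg/kg. The 150-500 mg mentioned in Sections 2.5 and 5.1 describes a typical administration and is not a bound. The 50-80 kg range is given as an average, not as an entry criterion.

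The reply on the form is stronger, and most of it stands. The form agrees with the planned single dose. It prints a formula to be completed by hand, not a volume. Section 6(B) itself orders the lower dose, and a physician injects slowly by hand with continuous feedback from the patient. Section 6 adds a stop rule: "If we observe a decline in blood pressure during the contrast media injection, we will discontinue the ferumoxytol injection immediately". A wrong dose would require a Section 6 change, a form left unrevised, and a physician following the form over the protocol.

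Two stronger readings are tempting, and the documents support neither.

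- A reader might infer that the records could not separate a full 4 mg/kg injection from a 5 mg/kg injection stopped at 80% of its volume. The entry on complete injection, the start and end times, and the recorded reactions largely settle that.
- A reader might infer that the analysis is compromised. Weight and the volume actually given are both recorded, so the delivered dose can be recovered as volume × 30 / weight.

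**Conclusion.** The point holds as a minor drafting gap in the dosing rules. The protocol names 510 mg Fe as the approved single-injection dose but does not apply it to the dose it plans to give, so a patient above 102 kg would exceed it. The 7.8% excess at 110 kg is an illustration. The documents give no weight distribution, so the number of patients affected is unknown and may be zero. The conclusion assumes that the 510 mg figure is meant as a limit on any single injection, which is how Section 6(C) describes it but not how it is applied.

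The form issue is secondary and conditional. The 25% excess and 16.7% shortfall arise only if Section 6(B) or 6(C) is invoked and the form is used unrevised. The documents do not support calling a dosing error likely, and nothing here bears on power, endpoints or analysis. This is a change the sponsor could make; the study does not depend on it.

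**What to change.** In Section 4, after the 5 mg Fe/kg dose, add: *not to exceed 510 mg Fe (17 ml) at any dose level*.

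On both copies of the administration form (Section 4 and Appendix B, part III), replace the pre-filled 5 mg/kg with a blank for the dose level in force, and give the volume as min(weight × current mg/kg, 510 mg) / 30 mg Fe/ml. At 80 kg this yields 10.7, 13.3 and 16.0 ml at 4, 5 and 6 mg/kg. At 110 kg it yields 14.7 ml at 4 mg/kg and 17.0 ml at 5 and 6 mg/kg.

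The cost is one sentence and two form fields, on each of two copies, submitted as a routine modification for IRB approval before use, as Section 10.2 requires. It uses only the protocol's own limit and dose levels, and changes no sample size, visit, scan or analysis.

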Of note, the PI of this proposed study has applied USPIO as MR contrast agents in phase II and III clinical trials in adult patients (11, 13, 14, and 20). These contrast agents are very well tolerated and show excellent safety profiles (5-8). The delivered iron dose via a typical ferumoxytol administration is in the order of 150-500 mg iron oxides (note that these are coated iron particles, not free iron), which is equivalent to or lower than the iron dose administered with one blood sample. USPIO are slowly metabolized in the liver and not excreted via the kidneys. Thus, they are safe to use in patients with renal insufficiencies and are not associated with any risk of nephrogenic sclerosis (a potential adverse event after injections of certain gadolinium chelates). Anaphylaxis or anaphylactoid reactions were reported in 0.2% of a subject, which is in the order of or lower compared to other MR contrast agents (see FDA report, ref. 6).

Figure 1: MR signal characteristics of bone marrow tumors with USPIO, as demonstrated in a patient with Non-Hodgkin's lymphoma after chemotherapy and GCSF therapy. (A) T1-weighted MR images before contrast media administration show a hypercellular reconverted bone marrow, which demonstrates diffusely decreased signal due to its high cellularity. Two focal lesions are noted (arrows). (B) T1-weighted MR images after intravenous administration of the USPIO ferumoxtran-10 (Sinerem / Combidex) do not show any T1-enhancement (positive contrast) of these lesions. (C) Precontrast STIR images show a relatively high signal of the hypercellular reconverted bone marrow with focal, more hyperintense lesions (arrows). (D) STIR images after intravenous administration of ferumoxtran-10 show a marked, diffuse T2-enhancement (negative contrast, signal loss) of the normal bone marrow due to phagocytosis of the agent by macrophages in normal bone marrow. Focal neoplastic lesions (arrows) contain no or few macrophages and stand out as bright lesions (arrows).

[figure not shown]
[figure not shown]

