The MR exam will be carried out in the Pediatric CT/MR Imaging facility at Lucile Packard Children's Hospital or in the MR imaging suite at the Lucas Center. Both imaging facilities have resuscitation equipment for intervention in case of a rare, but possible event of an allergic contrast agent reaction. Oxygen supply, emergency medications, a "drug box" and CODE cart are available on both sites. A state licensed M.D will be present in the magnet suite during all contrast media injections. In addition, a pediatric nurse with special training in contrast agent interventions will be present in the imaging facility and available to assist with emergency interventions. The Emergency Department of Stanford Hospital is within walking distance to the imaging facilities. In case of serious AEs, physicians in the ED are also immediately available to help with emergency interventions.

Warnings: i) Ferumoxytol may cause serious hypersensitivity reactions including anaphylaxis and/or anaphylactoid reactions. In clinical studies, serious hypersensitivity reactions were reported in 0.2% of subjects receiving Ferumoxytol. This frequency of hypersensitivity reactions is not higher compared to standard MR contrast agents, used for routine clinical MR scans.
 ii) Hypotension may follow Ferumoxytol administration. In clinical studies, hypotension was reported in 1.9 % of subjects.
 iii) Iron Overload. Ferumoxytol should not be administered in patients with iron overload.

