4.2 Criteria for Removal from Study

Criteria for removal from study:

- i) Incomplete MR images,
- ii) Image artifacts

- iii) Adverse reaction to contrast agent,
- iv) Upon request of Patient for exclusion from study
- v) Suspected patients of bone sarcoma or osteomyelitis with incorrect assignment to a pathology.

Patients removed from the study will be replaced in order to reach a total of 10 subjects for each pathology.

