10. REGULATORY CONSIDERATIONS

10.1 Monitoring plan

The Stanford Cancer Center Data and Safety Monitoring Committee (DSMC) will be the monitoring entity for this study. The DSMC will audit study-related activities approximately once per year to determine whether the study has been conducted in accordance with the protocol, local standard operating procedures, FDA regulations, and Good Clinical Practice (GCP). In addition, the DSMC will regularly review serious adverse events and protocol deviations associated with the research to ensure the protection of human subjects. Results of the DSMC audit will be communicated to the IRB and the appropriate regulatory authorities at the time of continuing review, or in an expedited fashion, as needed.

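### The study-ending rule for severe anaphylactoid reactions quotes a 1% background rate where the protocol elsewhere gives 0.2%, does not say whether removed reactors count, and asks for no pause after a first event

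*Combined protocol and SAP*

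**What the plan says.** Section 6 states the rule twice. Under the stopping rules for the study, item (B), the trial is terminated on this condition: "In case we observe an increased incidence of severe anaphylactoid reactions, i.e. more than one patient in our limited study population of 20 patients". The sentence before it says that such reactions are "reported in 1% of patients receiving Gd-based contrast agents and 1% of patients receiving ferumoxytol". Item (A) of the dose modification scheme, earlier in Section 6, sets the same count without a background rate.

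Other sections give a different rate for the same agent. Section 2.5: "Anaphylaxis or anaphylactoid reactions were reported in 0.2% of a subject". Section 4, under Warnings: "serious hypersensitivity reactions were reported in 0.2% of subjects receiving Ferumoxytol". Sections 5.1 and 7.1 repeat the Section 4 figure.

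Section 4.2 lists "Adverse reaction to contrast agent" among the criteria for removal and adds: "Patients removed from the study will be replaced in order to reach a total of 10 subjects for each pathology".

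There are other safeguards. Stopping rule (A) reads: "In case of any serious AE, that leads to persistent impairment of a study patient, the study will be terminated". Section 4 places a physician in the magnet suite at every injection, Section 7.2 sends adverse events to the IRB, and under Section 10.1 "the DSMC will regularly review serious adverse events".

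**The concern.** The rule treats more than one severe reaction as an increased incidence, and the only rate beside it is 1%. Section 2.5 attaches 0.2% to the same unqualified term, one fifth of that. The rule counts severe reactions only, so the 0.2% for serious hypersensitivity is the closer comparator. The choice of rate affects how one severe reaction looks to whoever reviews it. At 1% it is the sort of thing that happens by chance in a study this size; at 0.2% it is not.

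Nothing in the protocol requires injections to pause after a first severe reaction that leaves no lasting impairment. The next patient, aged 10 to 21 and receiving the agent off label, could be injected before anyone outside the study team has looked at the event.

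The base of the count is also unclear. If reactors are removed and replaced, more than 20 patients are injected, and the rule does not say whether those removed stay in the count. Section 11 defines an analysis population for the MR images but none for safety.

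**Working it through.** The protocol gives no operating characteristics for this rule, so there is no figure of its own to reproduce.

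**Inputs.** Planned number of patients, 20 (Sections 6 and 11.3.1). Threshold for termination, two or more severe reactions (Section 6). Background rate p, either 0.2% (Sections 2.5, 4, 5.1, 7.1) or 1% (Section 6). True rates of 5% and 10% are assumptions, used only to show how the rule behaves when the rate is high.

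**Formulas.** Exact binomial with n injected:

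- at least one: 1 − (1 − p)^n
- exactly one: n·p·(1 − p)^(n−1)
- at least two: the first less the second

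**At n = 20:**

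- p = 0.2%: at least one = 1 − 0.998^20 = 0.0392. Exactly one = 20 × 0.002 × 0.998^19 = 0.0385. At least two = 0.0007.
- p = 1%: at least one = 1 − 0.99^20 = 0.1821. Exactly one = 20 × 0.01 × 0.99^19 = 0.1652. At least two = 0.0169.

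| True rate | At least one | Exactly one | At least two (study ends) |
|---|---|---|---|
| 0.2% | 3.9% | 3.9% | 0.07% |
| 1% | 18.2% | 16.5% | 1.7% |
| 5% (assumed) | 64.2% | 37.7% | 26.4% |
| 10% (assumed) | 87.8% | 27.0% | 60.8% |

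The column for exactly one is where a review hold would act and the present rule does not, leaving aside reactions with persistent impairment, which end the study anyway.

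**How strong one event in 20 is.** The exact two-sided 95% interval runs from 1 − 0.975^(1/20) = 0.13% to 24.9%, and so includes 0.2%. The one-sided 95% lower limit is 1 − 0.95^(1/20) = 0.26%, just above 0.2%.

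**Effect of replacement.** At 0.2%, the chance of at least one event is 1 − 0.998^25 = 4.9% with 25 injected and 1 − 0.998^26 = 5.1% with 26. It passes 5% once six patients have been replaced. If severe reactors are replaced until 20 patients without such a reaction are reached, and everyone injected is counted, the study ends when two reactions fall among the first 21 injected: 0.08% at 0.2% and 1.9% at 1%. The count base therefore hardly changes the probabilities, provided removed patients are counted.

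**The case against.** The best reply is that the trigger is an explicit count. More than one means two, whichever rate is quoted, and dose modification item (A) states the rule with no rate. This stands: correcting 1% to 0.2% does not by itself change when the study ends. It changes only how a first event is read.

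The 1% could also be meant as a rate for all grades. It is not labelled severe, so the serious hypersensitivity figures in Sections 4, 5.1 and 7.1 do not directly contradict it. Section 2.5, however, uses the same unqualified term with 0.2%. And if 1% is for all grades, it is the wrong comparator for a rule on severe reactions.

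A hold after a first event is partly a design preference, given the safeguards already in place and slow accrual. It would not catch everything: at a true 1% it would never fire in 82% of studies. At an assumed 5% the present rule leaves the study running 73.6% of the time, but in 35.8% (0.95^20) there is no event for any rule to act on.

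A reader might infer more than the documents support:

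- *That a first severe reaction is already a safety signal at 0.2%.* This needs a one-sided 5% level, which the protocol does not set. It fails at 2.5% with 20 injected, and at 5% with 26 or more. The two-sided interval includes 0.2%.
- *That reaction incidence would be zero by construction, since reactors leave the final 20.* No section says that safety is counted or reported on that base. Section 4.2 can be read as restoring evaluable imaging subjects. The defect is ambiguity.
- *That severe has no meaning in the protocol.* Item (B) of the stopping rules for an individual test separates mild symptoms from severe or progressive ones by example. It gives no formal grade, and the study rule does not point to it.
- *That dose reduction could compete with termination.* Dose modification item (A) already says these reactions are not dose dependent and ends the study.

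**Conclusion.** The point holds as a correction and a cheap improvement to a safety rule; it is not a flaw in the design. The 1% beside the rule conflicts with the 0.2% in Section 2.5, and 0.2% is the better comparator on the protocol's own figures. With 20 injected, a first severe reaction has a 3.9% chance at 0.2% against 18.2% at 1%. At the lower rate it is unusual enough to deserve review before the next injection, but it is not enough to stop on. Termination at two is reasonable under either rate (0.07% and 1.7% by chance).

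The count base is unclear. The investigators probably mean every injected patient, and on that reading the rule works.

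The figures assume independent reactions with a common probability. They also assume that the 0.2%, which Section 2.5 cites from a report on adults with chronic kidney disease, applies to patients aged 10 to 21. The documents give no anaphylactoid rate for that age group.

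**What to change.** Make the same changes in both places in Section 6, dose modification item (A) and study stopping rule (B):

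1. Quote one background rate for severe reactions, with its source. On the protocol's own figures this is 0.2%. If the 1% is for all grades, label it so and do not set it beside this rule.
2. Replace the reference to a population of 20 with all patients who receive any ferumoxytol, including those later removed under Section 4.2.
3. Keep termination at two severe reactions, and the existing rule on persistent impairment.
4. After a first severe anaphylactoid reaction, hold further injections until the monitoring committee named in Section 10.1 has reviewed it.
5. For the meaning of severe, refer to the symptom list in item (B) of the stopping rules for an individual test, applied to reactions judged anaphylactoid. That qualifier matters because the list includes dizziness, which Section 7.1 places among common reactions (2% or more). An isolated event at 2% would occur at least once in 20 patients with probability 1 − 0.98^20 = 33%.

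The cost is a few sentences in Section 6, with a cross-reference in Section 4.2. A hold would arise by chance in 3.9% of such studies at 0.2%, or 18.2% at 1%. At the one to two patients a month expected in Section 11.3.1, a one-month hold would delay one or two patients.
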